 - Clinically significant CHD diagnosed by invasive or non-invasive testing (such as coronary angiography, stress test using treadmill, stress echocardiography, or nuclear imaging)Documented CHD risk equivalents (includes 1 or more of the following criteria):
 - Symptomatic peripheral arterial disease (PAD) defined as
 - peripheral vascular disease with symptoms of claudication or resting limb ischemia with either ankle brachial index <0.9 performed by a vascular lab or
 - angiogram (including computed tomographic angiography [CTA]) showing $\geq 50\%$ stenosis or
 - peripheral arterial revascularization (surgical or percutaneous) occurring greater than 90 days prior to Visit S1 or
 - abdominal aortic aneurysm confirmed by imaging or aortic aneurysm repair occurring greater than 90 days prior to Visit S1 or
 - lower extremity amputation due to peripheral vascular disease occurring greater than 90 days prior to Visit S1
 - Cerebrovascular atherosclerotic disease defined by:
 - ischemic stroke occurring greater than 90 days prior to Visit S1 or
 - Carotid endarterectomy, carotid stenting, or more than 70% stenosis in a carotid artery determined by carotid ultrasound or angiogram occurring greater than 90 days prior to Visit S1.

Note: Patients with T2DM are allowed in this study; however, for this study T2DM is not considered a CHD risk equivalent
7. Be on maximally tolerated lipid-modifying therapy, including a maximally tolerated statin either alone or in combination with other lipid-modifying therapies, at stable doses and regimens for at least 4 weeks prior to screening (6 weeks for fibrates; however, gemfibrozil is not allowed as per co-administration instructions defined in the statin label). Maximally tolerated statin includes statin

regimens other than daily dosing, including no to very low doses, but reasons for not using high-intensity statin dosing must be documented.

A patient's maximally tolerated lipid-modifying therapy will be determined by the investigator using their medical judgment and available sources, including the patient's self-reported history of lipid-modifying therapy.

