5. Uncontrolled hypertension, defined as sitting systolic blood pressure (SBP) \geq 160 mmHg and diastolic blood pressure (DBP) \geq 100 mmHg after sitting quietly for 5 minutes.
Note: If the initial blood pressure (BP) values meet or exceed the specified level, an additional BP assessment may be completed. If the systolic or the diastolic values continue to meet or exceed the threshold, the patient may not continue screening. However, at the discretion of the Investigator, the screening period (between Visits S1 and S2) may be extended up to 4 weeks to allow for a repeat qualifying BP assessment following adjustment of BP medication(s), provided that the patient has been on a stable dose of the BP medication for a minimum of 2 weeks prior to randomization and the repeat BP measurements do not meet the exclusion criteria.
6. Hemoglobin A_{1c} (HbA_{1c}) \geq 10% at Week -5 (Visit S1)
7. Uncontrolled hypothyroidism, including thyroid-stimulating hormone (TSH) $>$ 1.5 \times the upper limit of normal (ULN) at Week -5 (Visit S1). Patients stabilized on thyroid replacement therapy for at least 6 weeks prior to randomization are allowed.
8. Liver disease or dysfunction, including:

- Positive serology for hepatitis B surface antigen (HBsAg) and/or hepatitis C antibodies (HCV-AB) at Week -5 (Visit S1); or
 - Alanine aminotransferase (ALT), aspartate aminotransferase (AST) $\geq 2 \times$ ULN, and/or total bilirubin (TB) $\geq 2 \times$ ULN at Week -5 (Visit S1). If TB $\geq 1.2 \times$ ULN, a reflex indirect (unconjugated) bilirubin will be obtained and if consistent with Gilbert's disease or if the patient has a history of Gilbert's Disease, the patient may be enrolled in the study.
Note: At the discretion of the investigator, a single repeat of ALT and/or AST may be completed prior to randomization. For those patients who have a repeat ALT and/or AST, the repeat value will be used to determine eligibility. Also, if test for hepatitis C antibody is positive, but reflexive test for Hepatitis C ribonucleic acid (RNA) is negative, patient can be enrolled.
9. Gastrointestinal conditions or procedures (including weight loss surgery; eg, Lap-Band[®] or gastric bypass) that may affect drug absorption
 10. Hematologic or coagulation disorders or a hemoglobin (Hgb) level < 10.0 g/dL (100 g/L) at Week -5 (Visit S1)

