6.6. Patient Identification Numbers

A unique patient identification number will be assigned to each patient to identify each patient throughout the study and will be entered on all documentation. If a patient is not eligible to receive treatment, or if a patient discontinues from the study, their patient identification number cannot be assigned to another patient.

Patient identification numbers will be assigned sequentially by interactive web response system (IWRS) at the time of informed consent during the screening module transaction. Screening and Placebo Run-in Period

Screening will occur approximately 5 weeks prior to Day 1 (Visit T1) where the patient's eligibility will be evaluated. Eligible patients who are taking allowed concomitant medications must be on stable regimens as defined in [Section 8.2](#). At the investigator's discretion, screening (time between visits S1 and S2) may be extended for an additional 4 weeks if needed to adjust background medical therapy or for other reasons as specified in the protocol. Eligible patients will return to the clinical site at Week -4 (Visit S2) to initiate administration of single-blind (patient only) placebo. Eligible patients will return at Week -1 (Visit S3) for lipid and safety laboratories and an assessment of tolerability and study drug adherence (see [Section 7.1](#) and [Section 7.2](#) for eligibility criteria). Patients who are deemed not eligible for randomization at any point during screening will be notified by clinical site personnel regarding their eligibility status and considered screen failures. As necessary, for reasons of safety if a patient begins the run-in period but screen fails prior to randomization, the patient may be asked to return to the clinical site for further evaluation and follow-up of AEs.

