and S2) may be extended up to 4 weeks to allow for a repeat qualifying BP assessment following adjustment of BP medication(s), provided that the patient has been on a stable dose of the BP medication for a minimum of 2 weeks prior to randomization and the repeat BP measurements do not meet the exclusion criteria.

6. Hemoglobin A_{1C} (HbA_{1C}) $\geq 10\%$ at Week -5 (Visit S1)
7. Uncontrolled hypothyroidism, including thyroid-stimulating hormone (TSH) $> 1.5 \times$ the upper limit of normal (ULN) at Week -5 (Visit S1). Patients stabilized on thyroid replacement therapy for at least 6 weeks prior to randomization are allowed.
8. Liver disease or dysfunction, including:
 - Positive serology for hepatitis B surface antigen (HBsAg) and/or hepatitis C antibodies (HCV-AB) at Week -5 (Visit S1); or
 - Alanine aminotransferase (ALT), aspartate aminotransferase (AST) $\geq 2 \times$ ULN, and/or total bilirubin (TB) $\geq 1.2 \times$ ULN at Week -5 (Visit S1). If TB $\geq 1.2 \times$ ULN, a reflex indirect (unconjugated) bilirubin will be obtained and if consistent with Gilbert's disease or if the patient has a history of Gilbert's Disease, the patient may be enrolled in the study.

Note: At the discretion of the investigator, a single repeat of ALT and/or AST may be completed prior to randomization. For those patients who have a repeat ALT and/or AST, the repeat value will be used to determine eligibility. Also, if test for hepatitis C antibody is positive, but reflexive test for Hepatitis C ribonucleic acid (RNA) is negative, patient can be enrolled.

9. Gastrointestinal conditions or procedures (including weight loss surgery; eg, Lap-Band[®] or gastric bypass) that may affect drug absorption
10. Hematologic or coagulation disorders or a hemoglobin (Hgb) level < 10.0 g/dL (100 g/L) at Week -5 (Visit S1)
11. Active malignancy, including those requiring surgery, chemotherapy, and/or radiation in the past 5 years. Nonmetastatic basal or squamous cell carcinoma of the skin and cervical carcinoma in situ are allowed.
12. Unexplained creatine kinase (CK) $> 3 \times$ ULN at screening up to randomization (ie, not associated with recent trauma or physically strenuous activity). Patients with an explained CK elevation must have single repeat CK $\leq 3 \times$ ULN prior to randomization.

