- An optional visit between Visits S1 and S2 may be completed to determine eligibility if the patient's eGFR, ALT, AST, and/or TB meet exclusion criteria levels. If this optional visit is completed, the repeated value will be used to determine eligibility.
- Patients who are considered to be screen failures due to not meeting stability requirements for a condition or concurrent medication may be considered for rescreening after consultation with the Sponsor (or designee). These patients must be re-consented, re-registered in the IWRS, and will have a new patient ID number assigned.

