11.1.6.3.1. Monitoring and Management of Elevated Liver Function Tests

If at any time after randomization a patient experiences a new ALT and/or AST $>3 \times$ ULN, the patient will undergo repeat confirmatory liver function test (LFT) assessment as soon as is reasonably possible, preferably within 3 to 7 days of the laboratory result becoming available.

Repeat LFT assessment will include: 1) measurement of ALT, AST, alkaline phosphatase, total and direct bilirubin, prothrombin time (PT)/international normalized ratio (INR), eosinophil count, CK, antihepatitis A virus (total), HBsAg (confirmation of screening measurement), HCV (confirmation of screening measurement), and anti-cytomegalovirus/immunoglobulin M; 2) history of concomitant medication use; 3) history of exposure to environmental chemical agents, including ethanol; and 4) query for related symptoms. Additionally, further testing such as liver ultrasound or magnetic resonance imaging (MRI) scanning may be warranted to rule out additional pathology depending on clinical presentation and should be discussed with the Sponsor personnel or the authorized Medical Monitor.

- If repeat LFT assessment confirms ALT and/or AST $>3 \times$ ULN, consideration should be given to withdrawing the patient and administering no further doses of study drug. At the investigator's discretion, study drug may be interrupted and the patient rechallenged with study drug after LFTs have returned to baseline levels.
- If repeat LFT assessment confirms ALT and/or AST $>5 \times$ ULN, patient should be withdrawn from IMP treatment, but will be asked to continue to be followed for safety using the protocol-specified visit schedule (see [Appendix 1](#)) or more frequently if deemed by the investigator.
- If repeat LFT assessment confirms ALT and/or AST $>3 \times$ ULN in addition to any of the following, the patient should be given no further IMP treatment, but will be asked

to continue to be followed for safety using the protocol-specified visit schedule (see [Appendix 1](#)) or more frequently if deemed by the investigator:

- TB $>2 \times$ ULN

Note: In the case of patients with Gilbert's disease, TB will be fractionated and the determination of $2 \times$ ULN will be based upon direct (conjugated) bilirubin.

- INR $>1.5 \times$ ULN (unless the patient is on stable dose of anticoagulation medication)

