18.4. SAFETY LABORATORY EVALUATIONS

Results from the central laboratory will be included in the reporting of this study for Hematology, Blood Chemistry, Lipids, Coagulation, HbA1C, hsCRP and Urinalysis. A list of laboratory assessments to be included in the outputs is included in Protocol, Section 11.1.6.1.

Presentations will use SI Units and conventional units.

Quantitative laboratory measurements reported as “< X”, i.e. below the lower limit of quantification (BLQ), or “> X”, i.e. above the upper limit of quantification (ULQ), will be converted to X for the purpose of quantitative summaries, but will be presented as recorded, i.e. as “< X” or “> X” in the listings.

The formula to calculate eGFR is: $eGFR = 186 \times (\text{Creatinine} / 88.4)^{-1.154} \times (\text{Age})^{-0.203} \times (0.742 \text{ if female}) \times (1.210 \text{ if black})$, where creatinine is in mmol/L.

Summaries for all lab results, including unscheduled visit values, will be included for below analyses:
 Observed and change/percent change from baseline by visit (for quantitative measurements).

Shift from baseline by visit according to normal ranges.

Shift from baseline according to normal ranges for HbA1c and glucose by history of diabetes and visit.
 eGFR and values of CK will be summarized by treatment group and by baseline eGFR categories (low, normal, high).

Potential Hy’s law cases (>3 × ULN for either ALT or AST AND Total Bilirubin >2 × ULN in the setting of no known other cause) will be tabulated and listed.

Laboratory abnormalities in parameters of interest

- ALT or AST (> 3x ULN , >5xULN)
- TB (>2x ULN)
- CK (> 5x ULN) and (>10x ULN)
- Fasting Blood Glucose (≤50 mg/dL, ≥126 mg/dL) by history of diabetes
- HbA1c (≥6.5%) by history of diabetes
- Creatinine (change from baseline for >1 mg/dL)
- eGFR (< 15 mL/min/1.73m², 15 –< 30 mL/min/1.73m²)
- Hgb (decrease from baseline for ≥2 g/dL)
- Hgb (<8 g/dL)

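### The protocol prints conflicting eligibility rules, two of which (the total bilirubin cut-off and aortic aneurysm) change who may be randomized, and no clause says whether the synopsis or Section 7 governs

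*Protocol*

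**What the plan says.** **Bilirubin.** Synopsis exclusion 8 gives "and/or total bilirubin (TB) $\geq 2 \times$ ULN at Week -5 (Visit S1". Section 7.2, criterion 8, gives "and/or total bilirubin (TB) $\geq 1.2 \times$ ULN at Week -5 (Visit S1". Both then carry the same allowance, which begins in the synopsis "If TB $\geq 1.2 \times$ ULN, a reflex indirect (unconjugated) bilirubin will be obtained and if consistent with" and goes on to permit enrolment of patients with Gilbert's disease.

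**Aortic aneurysm.** Under symptomatic peripheral arterial disease, synopsis inclusion 6 lists "abdominal aortic aneurysm confirmed by imaging or aortic aneurysm repair occurring greater than 90 days prior to Visit S1 or". The matching list in Section 7.1, criterion 6, goes from peripheral revascularization straight to amputation.

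**Obesity medication.** Section 7.2, criterion 18, prints 44 weeks before randomization. Synopsis exclusion 18 prints 4 weeks, and Section 8.2.3 requires antiobesity drugs to be stable for at least 4 weeks.

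**Run-in adherence.** Criterion 19, in the synopsis and in 7.2, excludes adherence below 80%. Section 8.3 keeps patients at 80% or below from randomization.

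**Which text governs.** Section 6.6 tells the reader to "see [Section 7.1](#) and [Section 7.2](#) for eligibility criteria", and the same paragraph refers to Section 8.2 for stable concomitant regimens. Section 12.1 ranks the SAP over the protocol, but only for data analysis.

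**The concern.** These are operative thresholds, applied at about 125 sites. As printed, the same patient can be eligible on one page and a protocol deviation on another. A patient failing any entry criterion is a screen failure (Section 10.2.4), and failure to adhere to the protocol is a listed reason for closing a site (Section 7.4).

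The bilirubin cut-off also controls a procedure. Section 10.2.1 offers an optional repeat visit between S1 and S2 when "eGFR, ALT, AST, and/or TB meet exclusion criteria levels", so who may use that visit depends on which limit the site reads.

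The SAP plans to summarize screen failures by criterion category (Section 9), to list all deviations and to summarize major ones by treatment group (Section 10). Those outputs need one rule behind them.

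**Working it through.** **Power, as context.** The plan states more than 95% power with 500 and 250 patients, a difference of 15% and an SD of 15%. SE = 15 x sqrt(1/500 + 1/250) = 15 x sqrt(0.006) = 1.16. The difference is 15 / 1.16 = 12.9 standard errors, so power is about 1.00 and the stated figure holds. About 60 patients (40 + 20) would already give 95%. None of the disputed criteria enters this calculation.

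**The four pairs in current text:**

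| Rule | One reading | Other reading | Patients in dispute |
|---|---|---|---|
| Total bilirubin | excluded at >=2 x ULN (synopsis) | excluded at >=1.2 x ULN (7.2) | no Gilbert's disease, 1.2 to <2 x ULN |
| Aortic aneurysm or repair | qualifies (synopsis) | not listed (7.1) | no other qualifying HeFH, CHD or risk equivalent |
| Obesity medication | 4 weeks (synopsis, 8.2.3) | 44 weeks (7.2) | change more than 4 and up to 44 weeks before randomization |
| Run-in adherence | <80% excluded (criterion 19) | <=80% excluded (8.3) | exactly 80% |

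**Bilirubin.** The disputed band is 2.0 - 1.2 = 0.8 x ULN wide. The synopsis orders the reflex test and gives the Gilbert's permission from 1.2 x ULN, but does not say what happens to a patient without Gilbert's disease between 1.2 and 2. A permission to enrol is needed at 1.2 only if 1.2 would otherwise exclude. That favours 1.2, as does the 6.6 pointer to 7.2. No logged amendment touches criterion 8, so the logs do not help.

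The safety weight is limited. The stopping rule in 11.1.6.3.1 applies "If repeat LFT assessment confirms ALT and/or AST $>3 \times$ ULN in addition to any of the following", one of which is bilirubin above 2 x ULN. The SAP 18.4 Hy's law screen requires more than 3 x ULN "for either ALT or AST AND Total Bilirubin >2 × ULN in the setting of no known other cause". Bilirubin alone triggers neither.

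**Aneurysm.** Used only as evidence of intent, the Amendment 2 log names both the synopsis and Section 7.1 as the places where this item goes, and no logged change removes it. An accidental omission from 7.1 is the likelier explanation.

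**Obesity medication.** 44 - 4 = 40 weeks. Two current places say 4 and one says 44.

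**Adherence.** With S2 at Day -28 +/- 3, the run-in lasts about 25 to 31 days. Exactly 80% needs a whole number of tablets: 0.8 x 25 = 20 and 0.8 x 30 = 24 are possible. The nominal 28 days gives 0.8 x 28 = 22.4, which is not, and no other length in that range works. The synopsis design text asks for 80% compliance, which agrees with criterion 19.

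**The case against.** The strongest reply is that these are drafting slips with little consequence. Two items are close to trivial: 44 looks like a doubled digit, and the adherence conflict needs a patient at exactly 80%. Any disputed patient who is randomized stays in the full analysis set (SAP 5.2), and deviations are reported. All of that stands. It does not dispose of bilirubin and aneurysm, where the two texts admit different patients.

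Four stronger readings are tempting, but the documents do not support them.

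- *That 1.2 x ULN is proven to be the intended limit.* The reflex test at 1.2 is also a free-standing laboratory rule (Table 5, footnote a) and could coexist with an exclusion at 2. Section 7, which prints 44 weeks and lacks the aneurysm item, is not a reliable witness to intent. The Gilbert's permission makes 1.2 the better-supported reading, no more.
- *That a site following Section 6.6 is led to the wrong obesity-drug window.* The same paragraph refers to Section 8.2, where 8.2.3 gives 4 weeks.
- *That the blood-pressure criterion is a fifth conflict*, because criterion 5 joins systolic and diastolic limits with 'and' while its note uses 'or'. The wording is the same in the synopsis and 7.2. Section 10.2.1 and footnote 2 of the Schedule of Events provide for a repeat when either or both pressures are at exclusion level. With the note, these already point to an isolated elevation being exclusionary.
- *That the trial's inference is compromised.* Eligibility is settled before randomization and does not enter the power or testing plan.

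**Conclusion.** The conflicts are real and sit in current text. At least one place is wrong in each pair, and no precedence clause resolves them. Bilirubin (1.2 to <2 x ULN without Gilbert's disease) and aneurysm (patients with no other qualifying disease) change who is eligible and should be corrected. The 44-week figure is very probably a typing error, and the adherence mismatch affects only exactly 80%. Following Section 7 throughout is no cure: it gives the better-supported bilirubin limit but holds the likely errors on aneurysm and obesity medication.

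The number of patients affected cannot be derived. The conclusion assumes that the digits were read correctly from the PDF. For 2 against 1.2 and 4 against 44, a misread character cannot be wholly excluded from the text alone, but that would not explain a missing aneurysm item.

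**What to change.** Issue one clarifying amendment with a notice to sites:

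1. The sponsor confirms one bilirubin cut-off and prints it in both synopsis exclusion 8 and 7.2 criterion 8. The better-supported choice is 1.2 x ULN with the Gilbert's exception kept.
2. Add the aneurysm item to 7.1, or delete it from the synopsis if it was meant to be dropped.
3. Change 44 to 4 weeks in 7.2 criterion 18.
4. Change <=80% to <80% in 8.3.

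If enrolment has closed, record the same decisions in the deviation rules and the study report instead.

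The cost is a few words and a site communication. Choosing 1.2 x ULN may add a few screen failures at sites that used the synopsis limit. Sample size, visits and analyses do not change.

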7.3. Patient Lifestyle and Dietary Guidelines

Patients will be counseled to follow a lipid-lowering diet as per local or regional guidelines and should be encouraged (as able) to participate in a regular exercise program throughout the study.

7.4. Investigator/Sponsor Suspension or Termination of Patient Enrollment

If, in the opinion of the Investigator, the clinical observations in the study suggest that it may be unwise to continue, the Investigator may suspend or terminate the study after consultation with the Sponsor (or designee). A written statement fully documenting the reasons for such a termination will be provided to the Sponsor (or designee) and the Institutional Review Board (IRB) or Independent Ethics Committee (IEC).

The Sponsor has the right to terminate the study or to close a site and remove all study materials from the clinical site. A written statement will be provided to the Investigator, the IRB or IEC, and regulatory authorities, if required.

Possible reasons for termination of the study at a clinical site include, but are not limited to:

- Unsatisfactory enrollment with respect to quantity or quality
- Inaccurate or incomplete data collection on a chronic basis
- Falsification of records
- Failure to adhere to the protocol
- Lack of study oversight by the Principal Investigator and/or designee

If any serious or nonserious AEs have occurred at such a clinical site, all documentation relating to the event(s) must be obtained.

8. TREATMENT OF PATIENTS

8.1. Description of IMP

Table 4: Investigational Medicinal Products

Product Name:	Investigational Medicinal Product	
	Bempedoic acid	Placebo
Dosage Form:	██████████ tablets	██████████ tablets
Unit Dose:	180 mg	Not applicable
Container/Closure ^a	100-count bottle (depending upon visit) with screw on, childproof cap	35- and/or 100-count bottle with screw on, childproof cap
Route of Administration:	Oral, daily, with or without food	Oral, daily, with or without food
Physical Description:	██████████	██████████

^a A 100-day supply of IMP will be included in the 100-count bottle and a 35-day supply of single blind placebo lead-in will be included in the 35-count bottle.

Please see Pharmacy Manual for detailed storage requirements and instructions.

